1.1 Study Overview

This is a Phase 2 multicenter, double-blind, randomized, stratified, placebo-controlled study in end-stage renal disease (ESRD) subjects receiving hemodialysis at least 3 times per week for a minimum of 9 hours per week. Subjects will be stratified based on the diagnosis of documented atrial fibrillation (AF) at Screening (Yes/No), enrolled in PK substudy (Yes/No), enrolled in Platelet substudy (Yes/No), and then subjects will be randomized to 1 of 3 dose cohorts in a 1:1:1 ratio (Cohort A, Cohort B, and Cohort C). Within each dose cohort, subjects will be randomized in a 3:1 ratio to receive treatment with Study Drug (either ISIS 416858 or placebo).

Cohort A: 200 mg ISIS 416858 or placebo SC (3:1)

Cohort B: 250 mg ISIS 416858 or placebo SC (3:1)

Cohort C: 300 mg ISIS 416858 or placebo SC (3:1)

All cohorts will consist of up to 4-week screening period for procedures and a 26-week treatment period followed by a 12-week post-treatment evaluation period.

Approximately 204 subjects are planned to be enrolled in parallel in this study.

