2 ANALYTICAL PLAN

2.1 General Overview of Analyses

2.1.1 General Statistical Methods

Descriptive summary statistics including number of patients, mean, standard deviation, median, and range (minimum, maximum) for continuous variables, and counts and percentages for categorical variables will be used to summarize most data. All statistical tests will be conducted using 2-sided tests with 5% Type I error rate unless otherwise stated.

PK parameters will be summarized using number of patients, mean, standard deviation, coefficient of variation (CV), geometric mean, median, minimum, and maximum.

All analyses and tabulations will be performed using SAS® Version 9.2 or higher and Phoenix/WinNonlin version 6.1 or higher on a PC platform.

A separate analysis for on-treatment period might be provided if deemed necessary.

Pooled groups:

Patients who are placebo-treated will be pooled and analyzed as a single placebo group.

Patients who are ISIS 416858-treated may be pooled and summarized as the ISIS 416858 total group.

Baseline definition:

Unless otherwise specified, baseline for all safety laboratory results will be defined as the last non-missing measurement prior to the first dose. For post-dialysis Blood Urea Nitrogen (BUN) measures for Urea Reduction Ratio (URR) determination, post-dialysis baseline will be defined as the last non-missing post-dialysis measurement prior to the first dose

Analytical visits:

All post-baseline data will be summarized according to the visit windows in the table below. For patients who have multiple visits within a window, the average will be used in the summary for continuous variable and the worst case result will be used for categorical variable.

Table I Visit window for Clotting

Analysis visit	Visit window
Screening	<1
Baseline	last non-missing measurement prior to the first dose
Day8	[2, 11]
Day 15	[12, 21]
Day29	(22, 35]
Day43	[36, 49]
Day 57	[50, 63]
Day71	[64, 77]
Day 85	[78, 91]
Day99	(92, 105]

Day 113	[106, 116)
Day 120	[117, 126)
Day 134	(127, 140)
Day 148	(141, 154)
Day 162	[155, 168)
Day 176	[169, 182]
Day 190	(183, 196]
Day 204	[197, 210]
Day 218	[211, 224]
Day 232	[225, 238]
Day 246	(239, 252]
Day 260	[253, 266]

Table 2 Visit window for Vital Signs

Analysis visit	Visit window
Baseline	last non-missing measurement prior to the first dose
Day 5	(2, 6)
Day 8	[7, 9]
Day 12	[10, 13]
Day 15	[14, 17]
Day 22	[18, 25)
Day 29	[26, 32)
Day 36	[33, 39)
Day 43	[40, 46]
Day 50	[47, 53]
Day 57	[54, 60]

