The frequency and percentage of patients in each clotting category will be summarized by inspection site (air trap, dialyzer) for each visit including screening visit. The overall score for individual clotting category, which is the highest of the inspection site Air Trap and Dialyzer score, will also be summarized.

In addition, the frequency and percentage of patients for overall score in each clotting category will be summarized by the following visits:

Week 26 or ET results for patients completed Week 8.

The denominator is the number of patients with at least one non-missing clotting assessment for each specific period above. The overall score for individual clotting category (1, 2, 3, or 4) will be analyzed for treatment comparison between each of the ISIS-416858 Treated group and placebo group using the Wilcoxon Rank Sum test.

In addition, the overall score for individual clotting category (1, 2, 3, or 4) will be analyzed using the proportional odds model with treatment as main effect. The proportional odds model with treatment as main effect and baseline clotting category as covariate will also be provided. P-value, odds ratio, and 95% confidence interval will be provided.

At least one clotting category ≥ 3

The frequency and percentage of patients with at least one post-baseline clotting category 3 or greater event after Week 8 (Day 50) and up to last dose + 7 days will be summarized by treatment group for each of the following periods for subjects on treatment:

- Before Week 8
- After Week 8 and up to last dose + 7 days

The denominator is the number of patients with at least one non-missing clotting assessment after Week 8 and up to last dose+ 7 days. The corresponding Ex.act Binomial 95% confidence interval will be provided.

A logistic regression model with treatment as main effect will be used to test the treatment difference between ISIS 416858 versus placebo in the proportion of patients with at least one clotting category 3 or greater. An estimate of the odds ratio, p-value and two-sided 95% confidence interval will be computed from the model using Wald's test. The logistic regression model with treatment as main effect and baseline clotting category as covariate will also be provided.

In addition, the number of events across all subjects of dialysis circuit will be summarized by treatment group.

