Study Design	
This is a Phase 2, multi-center, stratified, randomized, double-blind, placebo-controlled study of ISIS 416858 (IONIS-FXIRXan Antisense Inhibitor of Factor XI) treatment for up to 26 weeks in ESRD patients receiving hemodialysis at least 3 times a week.
 
Subjects included in this study will maintain all of their standard of care dialysis treatments (including heparins) as determined by their treating practitioners.
 
Subjects will be stratified based on the diagnosis of documented atrial fibrillation at Screening, and then subjects will be randomized to 1 of 3 dose cohorts in a 1:1:1 ratio (Cohort A, Cohort B, and Cohort C). Additionally, the subjects will also be stratified based on their participation in the substudies (pharmacokinetic and/or platelet substudy) as applicable. Within each dose cohort, subjects will be randomized in a 3:1 ratio to receive subcutaneous treatment with Study Drug (either ISIS 416858 or placebo).
 
Cohorts A, B, and C
 
Patients in Cohort A will be randomized to receive once-weekly either 200 mg ISIS 416858 or placebo, subjects in Cohort B will be randomized to receive either 250 mg ISIS 416858 or placebo, and Cohort C will be randomized to receive either 300 mg ISIS 416858 or placebo.
 
The study will include a 4-week screening period for procedures and a 26-week treatment period followed by a 12-week post-treatment evaluation period. Subjects are encouraged to complete the entire treatment and post-treatment evaluation periods, even if Study Drug (ISIS 416858 or placebo) has been discontinued.
 
Upon completion of screening evaluations, including SC tolerability assessments with 0.9% sterile saline injections, eligible subjects will receive Study Drug weekly for the 26-week treatment period. All doses of Study Drug will be administered subcutaneously (SC) after completion of the hemodialysis treatment. Study Drug can be administered immediately after dialysis is completed when blood is returning to the subject but must be within 2 hours (preferably within 15 minutes of the conclusion of dialysis).

Number of Subjects	Approximately 204 patients are planned to be enrolled in parallel in this study and randomized equally across Cohorts A, B, and C.

PROTOCOL SYNOPSIS *Continued*

Study Population	Inclusion Criteria

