10.6.4 Pharmacodynamic Analysis

Pharmacodynamic analyses will be performed in the safety population. Change and percent change in FXI activity and antigen levels, aPTT, PT, and INR will be tabulated over time.

The extent and occurrence of clotting on the dialysis filters and circuit will be summarized descriptively by category scoring.

Table 5 Clotting Scale

Inspection Site	Category 1	Category 2	Category 3	Category 4
Air Trap	No clotting	Fibrinous ring with no clot formation on venous chamber filter	Clot formation on venous chamber	Coagulated system (treatment cannot continue without new setup)
Dialyzer	Clean dialyzer	Blood stripes affecting less than 5% of the fibers seen at the surface of the dialyzer	Blood stripes affecting 5% or more of the fibers seen at the surface of the dialyzer	Coagulated filter

Note: Overall score is the highest of the individual component scores

The relative occurrence of each clotting category will also be summarized from all obtained clotting assessments, whenever possible. Further details on the analysis of clotting assessments will be contained in the SAP.

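### No planned dose-versus-placebo test uses the four-category clotting score over repeated on-treatment sessions

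*Combined protocol and SAP*

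**What the plan says.** Both documents list the extent and frequency of clotting on the dialysis filters and circuit as a pharmacodynamic outcome (SAP 1.3.2, Protocol 10.1.2). The overall score at a session is the higher of the air trap and dialyzer categories, each 1 to 4. The table headed "Table I Visit window for Clotting" in SAP 2.1.1 sets the clotting visits.

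SAP 2.4 plans these analyses in the Per Protocol Population:

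- **Four categories, one score per patient.** The visit named for the overall-score comparison is "Week 26 or ET results for patients completed Week 8". A Wilcoxon rank sum test compares each dose with placebo. Then: "In addition, the overall score for individual clotting category (1, 2, 3, or 4) will be analyzed using the proportional odds model", without and with baseline clotting category.
- **All sessions after Week 8, as yes/no.** "A logistic regression model with treatment as main effect will be used to test the treatment difference" in the proportion of patients with at least one category 3 or higher, up to last dose + 7 days.
- **All on-treatment sessions, cut at 3.** Each patient's percentage of events in category 3 or higher is computed before and after Week 8, and the change is analysed by ANOVA. No factor is named.
- **Most severe category by FXI activity.** This is a summary in active-treated patients only.

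Protocol 10.6.4 adds a descriptive display: "The relative occurrence of each clotting category will also be summarized from all obtained clotting assessments, whenever possible". It leaves further detail to the SAP.

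**The concern.** Frequency of clotting is a property of repeated sessions, and extent is a property of the graded scale. Each planned comparison with placebo keeps at most one of the two. The ordinal tests keep the grades but see one session per patient. The analyses over all sessions keep the repetition but treat categories 1 and 2 as equal, and 3 and 4 as equal.

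At stake is how readily a real effect on circuit clotting would show in a dose-versus-placebo comparison of about 51 patients per arm, fewer after Per Protocol exclusions. The ungraded or unused sessions are already being collected, so any gain costs no patients or visits.

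**Working it through.** **1. Arm sizes.** Protocol synopsis: "Approximately 204 patients are planned to be enrolled in parallel in this study". SAP 1.1: "Within each dose cohort, subjects will be randomized in a 3:1 ratio to receive treatment with Study Drug". So 204/3 = 68 per cohort, 68 x 3/4 = 51 active per dose and 68 - 51 = 17 placebo. Pooled placebo is 3 x 17 = 51, which gives 51 vs 51 for each dose. SAP 2.1.1: "All statistical tests will be conducted using 2-sided tests with 5% Type I error rate unless otherwise stated".

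The plan states no power, effect size or clotting rate (SAP 2.1.3 gives no statistical rationale for the sample size). There is no planned figure to reproduce.

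**2. Sessions.** From the clotting windows, the post-baseline on-treatment visits are:

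- before Day 50: Days 8, 15, 29, 43 (4 visits);
- after Day 50: Days 57, 71, 85, 99, 113, 120, 134, 148, 162, 176 (10 visits).

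The ordinal tests therefore use 1 of 10 sessions after Week 8, or 1 of 14 on treatment.

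**3. What the unused sessions are worth.** With m = 10 sessions and within-patient correlation rho, the equivalent number of independent sessions is m/(1 + (m-1)rho).

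| rho | equivalent sessions | information lost by using one |
|---|---|---|
| 0.2 | 3.6 | 72% |
| 0.3 | 2.7 | 63% |
| 0.5 | 1.8 | 45% |
| 0.7 | 1.4 | 27% |

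The loss passes one half only when 10/(1 + 9 rho) > 2, that is rho < 4/9 = 0.44. The documents do not give rho.

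**4. Power under assumed rates.** Assumptions, none from the documents: cumulative-logit model with a patient random intercept of SD 1 or 2; odds ratio 0.5; ten sessions after Week 8; no missing data; 51 vs 51; two-sided 5%.

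| Test | Power |
|---|---|
| Wilcoxon, single session | 19-38% |
| Any category 3 or higher (Wald) | 18-45% |
| ANOVA on change in percentage of category 3 or higher | 9-61% |
| Mean score over all sessions, unadjusted | 34-83% |
| Mean score over all sessions, baseline-adjusted | 49-90% |

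Type I error of the mean-score tests is near 5%. The spread of the ANOVA depends largely on how much effect is already present before Week 8.

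A separate run of this kind used placebo shares for categories 1 to 4 of 40/40/17/3, 60/30/8/2 or 25/40/28/7%. It splits the result by SD. At SD 1 the single-session Wilcoxon has 29-38% and the unadjusted mean score 77-83%. At SD 2 they have 18-21% and 32-36%. Differences of a point or two from the table are simulation error.

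**5. Scale or repetition?** That run also tested each patient's share of sessions in category 3 or higher after Week 8, which is not a planned test. Power for share vs mean score was 66.4 vs 80.6, 48.7 vs 76.9 and 75.3 vs 83.1% (SD 1), and 27.7 vs 34.3, 21.6 vs 32.2 and 32.4 vs 36.0% (SD 2). Keeping the four grades therefore adds about 4 to 28 points (36.0 - 32.4; 76.9 - 48.7). The rest of the gain comes from using all sessions.

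**6. A second model.** A Gaussian copula with marginal odds ratio 0.5, rho 0.2 to 0.7 and a placebo rate of category 3 or higher of 10, 25 or 40% per session gives 37-48% for the Week 26 Wilcoxon and 27-58% for any category 3 or higher. The ANOVA has 27-92% with no effect before Week 8, and 11-41% with half the log odds ratio already present. The all-session mean score has 51-97%. With 40 per arm and rho 0.3 to 0.5, the Wilcoxon has 30-40% and the mean score 55-82%.

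**7. The ANOVA's subtracted period.** Dosing starts on Day 1, so Days 8 to 43 are all on drug. Protocol 2.4 expects meaningful anticoagulation after about 4 to 6 weeks of dosing. Day 29 is 28 days (4 weeks) and Day 43 is 42 days (6 weeks) after the first dose, so part of the effect may be subtracted.

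**The case against.** A reader might infer that most of the clotting data are lost to the placebo comparison. The documents do not support that. The ANOVA draws on every on-treatment session and on how often severe clots occur. The information lost by the single-session tests also depends on a correlation that is not stated (step 3). The ANOVA can even win: with no effect before Week 8, it beats the unadjusted mean score in 3 of 12 copula settings (for example 92.1 vs 64.4% at rho 0.7 and a 40% rate). With half the effect already present it loses in all 12.

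Cutting at category 3 is a reasoned choice. Protocol 2.2 cites the earlier dialysis study for reducing severe clotting events. If the drug acts only at that threshold, the all-session ordinal score has less power than the category-3 analysis (6-35% vs 20-43%), though no less than the single-session test (5-14%). The gains in step 4 assume a constant shift across all cutpoints and sessions.

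A reader might also take Protocol 10.6.4 to require an all-session test. It asks for a descriptive summary, and SAP 2.4 tabulates the categories at every visit. Nor would a null at Week 26 be uninformative, since the SAP reports an odds ratio with 95% CI.

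Finally, the SAP sentence before the Week 26 item speaks of visits, and a later one of periods, in the plural, while one item is listed. Run visit by visit, each test would still use one score per patient. An item covering several sessions would change this, but none is stated.

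All of this limits the size of the point. None of it supplies a placebo comparison that keeps four categories over repeated sessions.

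**Conclusion.** The gap is real and can be read directly from SAP 2.4: the ordinal tests use one session per patient, and the analyses over all sessions cut at category 3. The ANOVA is only a partial remedy, because it names no treatment factor or dose contrast and subtracts an on-drug period.

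The size is conditional. With odds ratio 0.5 and 51 per arm, the all-session ordinal score had more power than the single-session Wilcoxon in every proportional-odds setting tried. The gain is large if patients differ moderately (SD 1) and modest if they differ strongly (SD 2). Adjusting for baseline recovers part of the latter. These figures rest on assumed rates and a proportional-odds effect. The GEE model proposed below was not simulated; the mean score stands in for it.

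The synopsis and Appendix A call the clotting measure exploratory, and nothing in the trial is powered on it. The change is worth making because it is cheap, and not because a primary conclusion is at risk. There is no ground for dropping or demoting the Week 26 tests.

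**What to change.** In SAP 2.4:

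1. Add one all-session ordinal analysis. Fit the proportional odds model already planned (treatment, baseline clotting category) to all overall scores after Week 8 (Day 50) up to last dose + 7 days. Use GEE with robust standard errors clustered on patient. Report the odds ratio and 95% CI for each dose versus pooled placebo.
2. Name treatment as the factor in the ANOVA on change in percentage, with each dose versus pooled placebo.
3. Keep the Week 26/ET Wilcoxon and proportional odds tests and the category-3 analyses as they are.

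The cost is SAP wording and one more exploratory model on data already collected, with no new visits or patients. There are two downsides. The new estimate averages over the period after Week 8 and is not an end-of-treatment value. It would also have less power than the category-3 analyses if the drug acts only at the severe-clot threshold, which is why those stay.

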2.2 Demographic and Baseline Characteristics

Demographic and Baseline characteristics (including dialysis and ESRD disease characteristics e.g., age, gender, ethnicity, race, weight, height, BMI, Primary Cause of ESRD, Time Since the Start Date for Renal Replacement Therapy (First Ever)/ESRD First Transplant or First Dialysis Ever, Time since the Start Date for Hemodialysis (Most Recent)) obtained before the first study drug administration will be summarized using descriptive statistics by treatment group and all patients for ITT population, Safety Population.

Additional summaries will be provided for each substudy if there are adequate number of patients enrolled.

Age for each patient is defined as number of years between informed consent date and birth date.

For summarizing race, if multiple races are recorded in the database, then 'Multiple Race' is used in the summary table.

The study sample sizes will be summarized by trial unit (site) for enrolled patients. All patients with signed informed consent will be included in the enrolled patients.

Dialysis prescription characteristics (Days of the week dialysis is scheduled, prescribed number of sessions, prescribed duration, dry weight total, type of dialyzer to be used, type of vascular access, Location of Arteriovenous Fistula/Graft and Location of Catheter) will be summarized for ITT population, Safety Population. Additional summaries will be provided for each substudy population if there are adequate number of patients enrolled.

Medical history will be coded by Medical Dictionary for Regulatory Activities (MedDRA) Version 21.0. Medical history will be summarized by System Organ Class (SOC) and Preferred Term (PT). In addition, the frequency and percentage of patients with CHAOS score (0, 1, 2, ..., 6) will be provided for AF substudy population. The CHADS score is the total of the scores per the risk criteria below with data collected from Targeted Medical History CRF.

Score	CHADS2 Risk Criteria
1 point	Congestive heart failure
1 point	Hypertension
1 point	Age 75 years
1 point	Diabetes mellitus
2 points	Stroke/transient ischemic attack

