While dialysis patients suffer numerous thrombotic events, they also are at increased risk of bleeding events. ESRD is associated with attenuated platelet aggregation and adhesion, and altered blood rheology. In ESRD patients, blood vessels tend to be compromised from chronic comorbid medical diseases such as diabetes and hypertension, age, repeated phlebotomy and need for vascular access, and chronic exposure to anticoagulants such as heparin and antiplatelet agents that are given to maintain vascular access patency and reduce the risk of arterial thrombotic events. Contemporary estimates suggest that 1 out of every 7 chronic dialysis patients will be hospitalized for a hemorrhagic event within 3 years of starting dialysis and the risk of major bleeding doubles with the use of anticoagulants (Sood et al. 2014). Patients receiving dialysis are therefore at both high risk of thrombotic events and high risk of bleeding events. This has resulted in a clinical dilemma as the management of dialysis patients at the highest risk for thrombotic events. For example, patients receiving dialysis with concomitant atrial fibrillation are anticoagulated only 37% of the time in North America and only 1% of the time in Germany (Wizemann et al. 2010; Tan et al. 2017). Furthermore, the use of vitamin K antagonists in such patients has resulted in a 2-fold increase in the risk of major bleeding and even low-dose anticoagulation (target INR 1.5-1.9) resulted in a 1.5-fold increased risk of major bleeding (Elliott et al. 2007).

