3. EXPERIMENTAL PLAN

3.1 Study Design

This is a Phase 2 multicenter, double-blind, randomized, stratified, placebo-controlled study in ESRD subjects receiving hemodialysis at least 3 times per week for a minimum of 9 hours per week. Subjects will be stratified based on the diagnosis of documented atrial fibrillation (AF) at Screening (Yes/No), and then subjects will be randomized to 1 of 3 dose cohorts in a 1:1:1 ratio (Cohort A, Cohort B, and Cohort C). Additionally, subjects will be stratified by participation in the substudies. Within each dose cohort, subjects will be randomized in a 3:1 ratio to receive SC treatment with either ISIS 416858 or placebo (See [Study Design and Treatment Schema](#)). All standard of care hemodialysis therapies as prescribed by their providers, including heparins, will be continued.

Cohort A: 200 mg ISIS 416858 or placebo SC (3:1)
Cohort B: 250 mg ISIS 416858 or placebo SC (3:1)
Cohort C: 300 mg ISIS 416858 or placebo SC (3:1)

All cohorts will consist of up to 4-week screening period for procedures and a 26-week treatment period followed by a 12-week post-treatment evaluation period.

The SC Tolerability assessments using 0.9% sterile saline should be administered as 2 noncontiguous injections during the screening period on Study Days S-14 (\pm 3) and S-7 (\pm 3). Enrolled subjects will receive a SC dose of Study Drug (200 mg, 250 mg, or 300 mg ISIS 416858, or placebo) approximately weekly from Week 1 (Day 1) through Week 26.

The windows for study visits are specified in the Schedule of Procedures ([Appendix A](#)); please note that the Study Drug (ISIS 416858 or placebo) dose may not be administered more than once on the same day. Any questions on study procedures and visit windows may be directed to the Sponsor (or designee).

3.1.1 *Platelet Function/Activation Subgroup*

fu a subgroup of approximately 12 subjects in each cohort, platelet function and/or activation will be assessed. These subjects must have platelet counts that are $180,000/\text{mm}^3$ at Screening and who are not taking any anticoagulants or antiplatelet agents (other than aspirin).

At regularly scheduled visits during Weeks 1 (pre-dose), 12, 26, and 38, additional blood samples will be collected and processed for platelet function and/or activation tests as shown in [Appendix A](#).

3.1.2 *Pharmacokinetic Subgroup*

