 - More than 3 episodes of severe hypoglycemia requiring the assistance of another person to actively administer carbohydrate, glucagon or other resuscitative actions
 - One (1) event of hypoglycemia in which the patient required hospitalization
 - Recurrent syncope and recurrent hypotension in the inter-dialytic period requiring intervention

13. Planned major surgery in the next 6 months, including subjects receiving a kidney transplant or subjects that anticipate changing dialysis modality (i.e., hemodialysis to peritoneal dialysis).
14. Recent history of, or current drug or alcohol abuse as determined by the Investigator.
15. Concomitant use of anticoagulant/antiplatelet agents (e.g., warfarin, dabigatran, rivaroxaban, clopidogrel) that may affect coagulation (except low dose aspirin (≤ 100 mg/day) during Treatment and Post-treatment Evaluation Periods is not allowed. Stable doses of heparins during dialysis are permitted.
16. Uncontrolled hypertension as judged by the Investigator. For example, patients with a pre- or post-dialysis blood pressure (BP) that is > 180 mmHg on at least 3 of the last 5 dialysis treatments.
17. Have any other conditions, which, in the opinion of the Investigator or Sponsor would make the subject unsuitable for inclusion, or could interfere with the subject participating in or completing the study.

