8.6.3 Stopping Rule for Bleeding

If an event of Major Bleeding or CRNMB event occurs, the Investigator must notify the Sponsor Medical Monitor (or designee) and the subject should be closely monitored (vital signs, lab tests such as Hb, HCT and platelet count, additional outpatient visits, overnight stays and coagulation tests may be needed) throughout the treatment and during the post-treatment evaluation period.

In the event of Major Bleeding or CRNMB (see definitions in [Section 8.5.3](#)) as assessed by the Investigator, dosing of a subject with Study Drng (ISIS 416858 or placebo) may be stopped permanently. The follow-up schedule for any events meeting this discontinuation criterion will be determined, including the suitability of the subject for resumption of dosing by the Investigator in consultation with the Sponsor Medical Monitor (or designee).

Treatment Precautions:

Recommendations to manage bleeding in a patient will be provided to all study sites:

Specifically, if a patient has Major Bleeding or Clinically Relevant Non-Major Bleeding during the trial, the following measures are to be considered by the Investigators to control that bleeding:

1. Delay of the next injection or discontinuation of treatment in consultation with Sponsor Medical Monitor (or designee) per [Section 8.6.3](#).
2. Review and discontinue concomitant medications that could exacerbate bleeding.
3. Mechanical compression/ Surgical intervention/haemostasis.
4. General volume management: fluid replacement & hemodynamic support.
5. Transfusion (whole blood/packed cells/FFP/platelets).

If bleeding cannot be controlled by these measures, consider administration of one of the following procoagulants (according to the dosages advised in the package insert), FXI concentrate (Hemoleven®), Recombinant Factor Vila (NovoSeven®), or 4-factor concentrate (prothrombin complex concentrate).

ISIS 416858 treatment does not directly inhibit circulating FXI, only production of this clotting factor in the liver. Therefore, the dose of fresh frozen plasma (FFP) or factor concentrate given should aim to increase FXI activity above 0.3 U/mL and should recognize that the half-life of circulating FXI is approximately 50 hours when considering the potential need for re-administration. Additionally, the time necessary to obtain a FXI concentration locally and to infuse FFP should be taken into consideration.

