8.9.1 Concomitant Therapy

A concomitant therapy is any non-protocol specified drug or substance (including over-the-counter medications, herbal medications and vitamin supplements) administered between the signing of informed consent and the last protocol specified Post-Treatment Evaluation Period visit ([Appendix A](#)).

Allowed Concomitant Therapy

Any medications deemed necessary by the Investigator are allowed except those listed in the disallowed concomitant therapy. The use of stable doses of unfractionated heparin and low-molecular weight heparin during hemodialysis is allowed.

Disallowed Concomitant Therapy

Concomitant use of anticoagulant/antiplatelet agents (e.g., warfarin, dabigatran, rivaroxaban, clopidogrel) that may affect coagulation (except low dose aspirin(;;:100 mg/day) during Treatment and Post-treatment Evaluation Periods is not allowed.

For subjects in the platelet function/activation subgroup, use of any anticoagulants or antiplatelet agents (other than aspirin) is not allowed.

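### Heparin dose and dose changes are not shown by arm, and baseline heparin is in no clotting model, so the clotting and bleeding comparisons could be affected without a reader seeing it

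*Combined protocol and SAP*

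**What the plan says.** **Who sets heparin.** The Protocol Synopsis (Study Design) has subjects "maintain all of their standard of care dialysis treatments (including heparins) as determined by their treating practitioners". Protocol 3.1 agrees: "All standard of care hemodialysis therapies as prescribed by their providers, including heparins, will be continued". The only limit is stability. Exclusion criterion 15 (Protocol 5.2) says "Stable doses of heparins during dialysis are permitted", and Protocol 8.9.1 says "The use of stable doses of unfractionated heparin and low-molecular weight heparin during hemodialysis is allowed". Stable is not defined, and neither document says how a dose change is treated in the analysis.

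**Clotting analyses (SAP 2.4).** The Week 26 or early-termination ordinal score is compared by Wilcoxon test and by a proportional odds model, first with treatment alone. Then: "The proportional odds model with treatment as main effect and baseline clotting category as covariate will also be provided". The logistic model for at least one category 3 or higher event follows the same pattern. The ANOVA on the change in each patient's percentage of such events names no covariate. Heparin is not a randomization stratum (SAP 1.4).

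**What is displayed.** SAP 2.2 summarizes "Dialysis prescription characteristics (Days of the week dialysis is scheduled, prescribed number of sessions, prescribed duration, dry weight total, type of dialyzer to be used", then vascular access and its location; heparin is not on the list. The prescription changes named in SAP 1.3.4 are access, time on dialysis and dry weight, and SAP 2.6 only lists them. SAP 2.3.8 tabulates concomitant drugs by ATC class and generic name, which shows use but not dose.

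**The concern.** The protocol itself ties heparin to both outcomes. Protocol 2.2 names "chronic exposure to anticoagulants such as heparin and antiplatelet agents" among the reasons why dialysis patients bleed, and describes a possible reduction in heparin need as an aim of the drug's development. Blinding does not prevent a reaction to a clotted circuit, because staff see the circuit whatever the arm. If the drug works, more placebo circuits clot. If practitioners respond with heparin, placebo patients then get more of it. That would lower later placebo clotting and could raise placebo bleeding.

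There is also a route from bleeding. After MB or CRNMB, Protocol 8.6.3 lists among the measures to consider: "Review and discontinue concomitant medications that could exacerbate bleeding". Stopping heparin after such a bleed cannot undo that patient's MB plus CRNMB event. It could affect a later first major bleed after a CRNMB, and later clotting.

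At stake is the reading of the clotting results and of the primary safety outcome. A small clotting difference, or similar bleeding rates, could reflect the drug or different heparin exposure, and the planned tables would not tell these apart.

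**Working it through.** The plan has no figure to reproduce. SAP 2.1.3 gives no statistical rationale for the sample size, and no clotting rate or heparin effect is stated. What follows is an illustration.

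**Inputs**
- n = 10 assessments after Week 8, from the clotting windows in SAP 2.1.1: Days 57, 71, 85, 99, 113, 120, 134, 148, 162 and 176.
- p = chance of category 3 or higher per session: 0.20 placebo, 0.10 active (assumed).
- r = single chance that heparin is raised after the patient's first such event: 0.3, 0.5 or 0.8 (assumed).
- Later risk is halved once heparin is raised; sessions are otherwise independent; no dropout (assumed).

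**Formulas**
- Expected sessions left after the first event: S = 10 − [1 − (1 − p)^10]/p. Placebo: 10 − 0.8926/0.20 = 5.537. Active: 10 − 0.6513/0.10 = 3.487.
- Mean session rate: p − r × S × (p/2)/10.
- Patients with heparin raised: r × [1 − (1 − p)^10].
- Last-visit rate: p × {1 − (r/2) × [1 − (1 − p)^9]}.

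**At r = 0.5**
- Session rate, placebo: 0.20 − 0.5 × 5.537 × 0.10/10 = 0.1723. Active: 0.10 − 0.5 × 3.487 × 0.05/10 = 0.0913. Difference −8.1 points.
- Heparin raised: 0.5 × 0.8926 = 44.6% v 0.5 × 0.6513 = 32.6%.
- Last visit: 0.20 × (1 − 0.25 × 0.8658) = 15.7% v 0.10 × (1 − 0.25 × 0.6126) = 8.5%.

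| r | Session rate, placebo v active | Difference (points) | Last visit, placebo v active | Odds ratio at last visit |
|---|---|---|---|---|
| 0 | 20.0% v 10.0% | −10.0 | 20.0% v 10.0% | 0.44 |
| 0.3 | 18.3% v 9.5% | −8.9 | 17.4% v 9.1% | 0.47 |
| 0.5 | 17.2% v 9.1% | −8.1 | 15.7% v 8.5% | 0.50 |
| 0.8 | 15.6% v 8.6% | −7.0 | 13.1% v 7.5% | 0.54 |

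Differences and odds ratios use unrounded rates. The odds ratio is [q/(1 − q)]/[p/(1 − p)], with p and q the last-visit placebo and active rates.

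**How this maps to the planned analyses**
- The session rate is the post-Week 8 part of the ANOVA on percentages.
- The last visit corresponds to the Week 26 comparison, cut at category 3.
- The logistic endpoint is 1 − (1 − p)^10 = 89.3% v 65.1% at every r, because an increase that follows a first event in the window cannot remove that event. It would move only if heparin changed before the window, or without a category 3 or higher event in it.

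**Bleeding.** No rate is documented. If MB plus CRNMB were 6% placebo v 12% active (RR 2.00), a 2-point heparin-related rise on placebo gives 12/8 = 1.50. With a 2-point fall on active as well, it is 10/8 = 1.25. These shifts are assumed outright and only show sensitivity.

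**The case against.** The strongest reply is that drug plus usual dialysis care against placebo plus usual care is a legitimate comparison. Heparin is background care in both arms, and under that estimand a heparin response is part of the outcome, not a bias. Randomization balances baseline heparin in expectation, and baseline clotting may already carry some of its information. This stands: the missing covariate is not an error, and how well baseline heparin predicts clotting is not documented. It does not remove the need to see heparin by arm, since a usual-care effect cannot be interpreted without knowing what that care was.

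Second, the stable-dose wording and the Per Protocol Population may limit the problem. SAP 2.4 analyses clotting in that population, which excludes major violations. But neither document says whether a heparin change is one. The notes to file listed in Protocol 1.1 include one on disallowed medication and the Per Protocol Set, whose content is not given. If a change did exclude patients, those who clotted could be removed after randomization, unequally by arm.

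Third, a practitioner can prescribe a dose that is then kept stable, so the heparin passages are not in flat contradiction. That is fair. They leave open what happens when the practitioner changes the dose.

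Fourth, the protocol calls circuit clotting exploratory, and heparin use will be visible by generic name. Both are true. The gap is dose and dose change.

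**Conclusion.** The gap in the text is established: no heparin term in any clotting model, no heparin dose or change by arm, and no definition of stable. The consequence is possible, not demonstrated. Under the assumptions shown, the session-level difference shrinks from 10 points to between 8.9 and 7.0, and the last-visit odds ratio moves from 0.44 to between 0.47 and 0.54. The size depends wholly on assumed rates, reaction and heparin effect.

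A reader might infer three stronger things that the documents do not support:
- **That every clotting result is biased.** The endpoint of at least one category 3 or higher event is unchanged by increases that follow a first event in its window.
- **That heparin changes must hide bleeding caused by the drug.** No bleeding rate or heparin effect is documented, and the distortion could run either way.
- **That a reader could see nothing about heparin.** Use by arm will be tabulated.

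This is an inexpensive addition needed to interpret the results, not a proven analysis error.

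**What to change.** 1. In SAP 2.4, add baseline heparin (none, unfractionated or low-molecular-weight; dose per session if captured) beside baseline clotting category in the proportional odds and logistic models. This deals with chance baseline imbalance and may add precision; it does not deal with later changes. Do not adjust for post-randomization heparin, which treatment may itself affect.
2. Tabulate heparin dose, and the percentage of patients with an increase, decrease or stop from baseline, by arm, beside the clotting and MB plus CRNMB tables. This output makes any imbalance visible.
3. Reconcile the passages leaving heparin to the practitioner with those allowing stable doses. State before unblinding whether a heparin change affects Per Protocol membership. No clinical rule on heparin is proposed here.

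A sensitivity analysis counting a heparin increase as a clotting failure is optional. It mixes a practice decision with an observed outcome, so its value is debatable.

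Cost: SAP wording and one or two outputs. Protocol 8.9 already requires concomitant therapy on the eCRF. If dose per session is not captured, one more field is needed; the dialysis run-sheets named in Protocol 9.3.1 are a possible source.
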